### **Midway Drug Intervention Assessment (Visit 5)**

**Visit 5 (Midway):** On-site assessment to assess safety and abbreviated functional assessment during the 12-week intervention phase. Participants will be asked to fast for at least 8 hours prior to arrival.

The following procedures and assessments will be completed:

1. Interval history, vital signs, and a brief physical exam.
2. IV line will be placed
3. Dose Monitoring:
  - a. Subject will take morning dose of study drug
  - b. Research Blood assessments at baseline (before study drug), 30 minutes, 60 minutes:
    - i. Nitrite/Nitrate Serum Levels and other Research Bloods: baseline, 30 minutes, 60 minutes
    - ii. Platelet Mitochondrial Respirometry: baseline (before study drug), 30 minutes
    - iii. Research Inflammatory Indices: baseline (before study drug)
    - iv. CBC (for safety assessment)
4. pK assessments as in Visit 4 with orthostatic hypotension assessment Blood Pressures.
5. Functional evaluation:
  - a. Participants will complete the following:

- i. Steady-state walk, 400-meter corridor walk (with VO2 assessment), SPPB, Handgrip Strength
- ii. Participants will complete the Steady-state walk test 30minutes(+/-10 minutes from the 30 minute blood collection)
6. Additional study drug capsules distributed if needed
7. A breakfast will be provided after the 60-minute blood draw
8. 7-Day Home Activity Monitoring

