#### **Visit 7**

Participants will be encouraged to eat a light breakfast prior to arrival. The participants will be asked to take their study drug 30 minutes prior to the submaximal CPET.

Interval history, vital signs, and a brief physical exam.

See visit 2 for details.

1. Steady-State Walking Test
2. Submaximal CPET
3. Handgrip Strength Assessment.

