We will employ the same analytic strategy described above for the primary outcome mitochondrial respiration for each of our remaining secondary continuous outcomes of mitochondrial bioenergetics, skeletal muscle perfusion and clinical measures collected only pre- and post-intervention. The magnitude and statistical significance of the nitrite vs placebo contrasts will serve as formal tests of the hypotheses H1b-c and H2a-b.

**Aim 2:** For physical function and activity measures additionally assessed midway, and hypothesis H3a, we will instead employ a linear mixed model to accommodate multiple post-randomization assessments and the resulting stochastic non-independence of observations. Specifically, we will fit a series of linear mixed models with change from baseline in each measure of physical function/activity as the dependent variable; intervention arm (nitrite/placebo), follow-up time (mid-course assessments and 12 weeks) and their interaction as fixed effects; baseline value of the dependent variable as a fixed-effect covariate; and a participant random effect to account for multiple observations from each participant. We will appropriately construct means contrasts to make comparisons between intervention arms at each of the follow-up time-points, and interpret their statistical significance as supporting hypothesis H3a.

**Aim 3 (hypothesis H3b) Analysis:** We will examine whether changes in mitochondrial energetics, muscle perfusion and physical function/activity/fatigability tend to move at least partially in unison. We will compute Pearson and Spearman rank correlations between pre- to post-treatment changes in the above measures over the treatment period. We will consider correlations both with and without stratification by treatment group. We will also consider adjusting for baseline values of the measures considered and obtain partial correlation coefficients to isolate the associations in changes above and beyond any cross-sectional associations at baseline and comparing the correlations between groups using the Fisher's z-transformation. Finally, we will explore multivariable linear regression models with change in measures of physical function/ac-

tivity as the dependent variable; treatment group, and baseline and changes in measures of mitochondrial energetics as independent variables, taking care not to exceed the number of independent variables that could be realistically afforded by the effective sample size.

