**Sensitivity Analyses:** We will perform a series of sensitivity analyses to ensure the robustness of our results against various assumptions. One such analysis will involve inclusion of gender and baseline participant characteristics significantly different between groups as additional covariates in the ANCOVA and linear mixed models above. Another will involve sensitivity of results to missing data handling techniques. In addition, if analyses of residuals from the models show violations of statistical assumptions, we will consider fitting models after Box-Cox transforming the continuous variables.

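### The H3a mixed model implies one standard error for the arm contrast at both follow-up visits; if the visit variances differ, one visit's test is too liberal and the other's too conservative

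*Combined protocol and SAP*

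**What the plan says.** The model is in section 2.4.2, in the paragraph labelled Aim 2, although it serves hypothesis H3a.

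- **Outcome:** "change from baseline in each measure of physical function/activity as the dependent variable".
- **Fixed effects:** arm, "follow-up time (mid-course assessments and 12 weeks) and their interaction as fixed effects", plus the "baseline value of the dependent variable as a fixed-effect covariate".
- **Random part:** "a participant random effect to account for multiple observations from each participant".
- **Inference:** the plan will "make comparisons between intervention arms at each of the follow-up time-points, and interpret their statistical significance as supporting hypothesis H3a".

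The paragraph names no residual covariance structure, visit-specific variance, baseline-by-time term, robust standard error or degrees-of-freedom method. The only remedy named for violated model assumptions comes under Sensitivity Analyses: "we will consider fitting models after Box-Cox transforming the continuous variables".

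The timetable in section 2.2.2 marks the 400-metre walk, steady-state walk, SPPB and handgrip at the midway visit. Home activity monitoring is listed in the Visit 5 description but is not marked at midway in the timetable.

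**The concern.** A single participant random effect with default residuals is compound symmetry: one variance shared by both visits and one covariance between them. That is a strong assumption when the reported results are two visit-specific contrasts, because each contrast then borrows the other visit's variance.

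The visits are not run alike. For Visit 5 the instruction is "Participants will be asked to fast for at least 8 hours prior to arrival", and the functional tests are done in that one session with no maximal CPET. For Visit 7 it is "Participants will be encouraged to eat a light breakfast prior to arrival", and at Visit 6 the 400-metre walk is listed after the maximal CPET. Participants are also encouraged from Visit 4 to start or extend a walking routine as tolerated, so individual courses may diverge. These facts make equal variance something to relax rather than assume. They do not show that it fails.

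At stake is the error rate of every H3a contrast for the measures taken at both visits. Significance at either visit is to be read as support for H3a, so a liberal test at one visit matters whichever visit it is.

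**Working it through.** **The plan's own figure.** The documents give no SD, correlation or power for the H3a model. Their detectable difference is for the primary outcome. A noncentral-t calculation with 30 per arm and SD 97.61 reproduces it: 71.80 pmol/min/mg at 80% power, d = 71.80/97.61 = 0.736. It does not bear on this point.

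**Step 1: what the model estimates.** Take two visits, complete data (as in each imputed dataset), visit residual variances v1 and v2, and covariance c. Let M be a participant's mean over the two visits and D the difference between them. The arm contrast at either visit is the contrast in M plus or minus half the contrast in D. The random-intercept model gives both versions the same variance, proportional to

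Var(M) + Var(D)/4 = (v1 + v2 + 2c)/4 + (v1 + v2 − 2c)/4 = (v1 + v2)/2.

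The correct variances are proportional to v1 and v2 respectively. Each contrast therefore uses the average of the two.

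**Step 2: size.** Let k be the residual SD at the noisier visit divided by that at the quieter one. This is an assumption, since the documents give no visit SDs. The ratio of model SE to true SE is

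- quieter visit: f = √((1 + k²)/2)
- noisier visit: f = √((1 + k²)/2)/k

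and type I error is 2(1 − Φ(1.96·f)). For k = 1.25, √((1 + 1.5625)/2) = 1.132 and 1.132/1.25 = 0.906.

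| k | SE ratio, quieter / noisier | Type I error, quieter / noisier |
|---|---|---|
| 1.0 | 1.00 / 1.00 | 5.0% / 5.0% |
| 1.1 | 1.05 / 0.96 | 3.9% / 6.1% |
| 1.25 | 1.13 / 0.91 | 2.7% / 7.6% |
| 1.5 | 1.27 / 0.85 | 1.3% / 9.6% |
| 2.0 | 1.58 / 0.79 | 0.2% / 12.1% |

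**Step 3: simulation under no effect.** Settings: 30 per arm, complete data, assumed within-person correlation 0.5, 10,000 runs per scenario. Each cell is quieter / noisier visit; at k = 1.0 the two visits are alike and the order is midway / late.

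| k | Model SE (both visits) | Empirical SE | Rejection, planned model |
|---|---|---|---|
| 1.0 | 0.259 | 0.260 / 0.257 | 4.9% / 4.6% |
| 1.25 | 0.293 | 0.261 / 0.325 | 2.7% / 7.6% |
| 1.5 | 0.330 | 0.265 / 0.390 | 1.4% / 9.8% |
| 2.0 | 0.409 | 0.260 / 0.516 | 0.2% / 11.9% |

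The comparator was an unstructured covariance with baseline-by-time, which for complete data equals a separate ANCOVA at each visit. It rejected in 4.6% to 5.3% of runs at both visits in every scenario. One dataset with k = 1.5, fitted in standard mixed-model software, gave an arm-contrast SE of 0.340 at both visits, against per-visit ANCOVA SEs of 0.284 and 0.391.

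**Step 4: which term is responsible.** With equal residual SDs but baseline slopes of 0 and −0.6, the common slope settles near −0.3. It adds 0.3² = 0.09 to the residual variance at both visits alike (√1.09 = 1.04). Simulated type I error stayed at 5.3% and 4.8%. The empirical SE rose from 0.260 to 0.274 at the midway visit, about 5%. In this case the single baseline slope costs precision; the equal-variance constraint comes from the random intercept.

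**The case against.** **The residual structure is unstated, not fixed as equal.** This is true. The plan does not say that the random effect is the only covariance component. But a model listed with a participant random effect and nothing more would ordinarily be fitted as compound symmetry. Leaving the choice until the data are seen would weaken pre-specification.

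**The direction is unknown.** A reader might infer that the end-of-treatment contrast is the one inflated, on the ground that baseline predicts a 6-week value better than a 12-week one. The documents do not support that. They describe the post-drug visits as broadly repeating the baseline ones: Visit 6 refers back to Visit 1 and Visit 7 to Visit 2, with similar meal instructions and test order. The fasted Visit 5 is the odd one out, so baseline could equally predict the late visit better. Assumed baseline correlations of 0.8 midway and 0.5 late, with equal SDs, give residual variances of 0.38 and 0.77 and type I error of 1.6% midway and 9.0% late. Reversing the correlations reverses the errors. This objection stands.

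**Fasting and test order may shift only the mean.** The time effect would absorb such a shift, and no figure in the documents shows a change in variance. This also stands: the design differences are grounds for not assuming equality, not evidence of inequality.

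**The effect may be small.** At k = 1.1 it is about one percentage point. That stands too.

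**Other provisions might repair it.** They do not. Box-Cox is optional and does not give each visit its own variance. Multiple imputation fits this same model to each completed dataset. The simulation above used complete data without an imputation step, so its figures describe the within-dataset test.

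**Conclusion.** The point holds conditionally. On the standard reading, the H3a model gives both visit contrasts one standard error. Where the residual variances differ, the noisier visit is tested too liberally and the other too conservatively. The distortion is nil at equal variances, small at an SD ratio of 1.1, and material from about 1.25 (7.6% and 2.7%). These ratios are assumptions, and the documents fix neither the size nor the sign.

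Two further inferences should be resisted. The common baseline slope does not itself force equal variances. Nor does the problem reach the primary analysis: H1a and every measure taken only before and after treatment use ANCOVA. The affected outcomes are secondary or exploratory: the 400-metre walk, steady-state walk, SPPB and handgrip, and home activity if it is collected at Visit 5. The change is worth making because it removes the dependence on an untested assumption at almost no cost.

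**What to change.** In section 2.4.2, replace the participant random effect in the H3a model with an unstructured 2x2 within-participant covariance over the two follow-up visits (in SAS, a REPEATED statement with TYPE=UN) and Kenward-Roger degrees of freedom. Keep the arm-by-time terms and the same contrasts at each visit. As a secondary refinement for precision, add a baseline-by-time term.

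The cost is one extra covariance parameter (three instead of two) and one extra fixed effect, with 60 anticipated completers of 70 randomised. No new data, visits or participants are needed. If the unstructured form was already intended, the sentence is still needed so that the choice is on record before the data are seen.

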**H3b:** Changes in mitochondrial energetics and skeletal muscle perfusion induced by nitrite will be associated with changes in daily activity (measured by accelerometry), and fatigability (measured by rate of perceived exertion during steady-state [1.5 mph] walking).

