## **2.4 STATISTICAL ANALYSIS**

### **2.4.1 Sample Size Justification**

The principle focus of the proof of mechanism trial is the impact of nitrite on mitochondrial energetics. To detect a significant difference in mitochondrial state 3 respiration in permeabilized fibers (the primary outcome for Aim 1), the planned sample size is 35 per group (a total of 70 participants). Respiration data from a previous multi-site RTC that was co-led by [name], showed a baseline values of  $270.30 \pm 99.80$  pmol/min/mg (mean  $\pm$  standard deviation) for State 3 respiration and a pre- to post-intervention change of  $68.5 \pm 97.61$  pmol/min/mg We conservatively anticipate a dropout rate of approximately 14%. Using published methods implemented in commercial software (PASS 2012®, Number Cruncher Statistical Systems, Kaysville, Utah), with 70 patients and 60 anticipated completers, we will be able to detect statistical significance of a difference as small as 71.80 pmol/min/mg in pre- to post-nitrite change with 80% power in a 2-tailed test at the  $\alpha=0.05$  level. The criterion for a minimally clinically important difference (MCID) has not been authoritatively established for the measure, but the above detectable difference corresponds to a moderate to large effect size ( $d=0.74$ ) by Cohen's criterion. Therefore, the planned sample size affords an appropriate level of statistical sensitivity to address the aims in a mechanistic study with proximal biological outcomes such as ours.

For Aim 3, with the anticipated 30+30 completers, we will be able to detect statistical significance of correlations as small as 0.49 and 0.35, respectively, between changes in mitochondrial energetics and changes in physical activity/function and fatigability with 80% power in two-tailed tests at  $\alpha=0.05$  conducted without and with stratification by treatment group. As such, the planned sample size will afford sufficient statistical sensitivity to detect even moderate associations between mitochondria respiration and clinical endpoints.

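### The unstratified H3b correlation mixes between-arm and within-arm association, and the plan names no arm-adjusted analysis over all completers as the one that carries H3b

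*Combined protocol and SAP*

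**What the plan says.** Section 1.2 words H3b as follows: "Changes in mitochondrial energetics and skeletal muscle perfusion induced by nitrite will be associated with changes in daily activity", and the sentence goes on to fatigability.

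The Aim 3 (H3b) paragraph of section 2.4.2 plans five things:

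- Pearson and Spearman correlations between pre-to-post changes;
- each of these in two versions: "We will consider correlations both with and without stratification by treatment group";
- possibly, partial correlations given the baseline values of the measures (arm is not listed);
- a Fisher z comparison of the correlations between the groups;
- exploratory multivariable regressions of change in function or activity on treatment group and on baseline and change in mitochondrial energetics.

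None of these is singled out as the analysis on which H3b rests.

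Section 2.4.1 gives the sensitivity. It opens with "For Aim 3, with the anticipated 30+30 completers" and continues "we will be able to detect statistical significance of correlations as small as 0.49 and 0.35, respectively", for tests "conducted without and with stratification by treatment group".

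**The concern.** H3b is of interest because it adds something to H1a and H3a: whether participants whose energetics or perfusion change more are also those whose activity or fatigability change more. A correlation over both arms that ignores arm does not isolate that question. When nitrite moves the mean of both measures, the two arms form two displaced clouds, and the displacement alone produces a correlation. Baseline adjustment cannot remove it, because the shift arises after randomization.

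The problem therefore appears in the scenario the trial hopes for, with respiration improved (H1a) and activity or fatigability improved (H3a). A significant unstratified correlation could then be reported as evidence of an individual-level link when it partly repeats the two arm contrasts. The plan also gives no order of precedence among its H3b analyses, so nothing stops that result from being the one put forward.

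**Working it through.** **Inputs from the documents.** 30+30 completers, two-sided alpha 0.05, 80% power, detectable correlations 0.49 and 0.35, and a detectable respiration difference of 71.80 against a change SD of 97.61 (section 2.4.1); 1:1 allocation (section 2.3.10).

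**Assumption.** The documents give no nitrite effect on activity or fatigability. A standardized effect d2 is therefore varied. The respiration effect d1 is set at 0.74, which is the plan's detectable effect and not a forecast.

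**Step 1: reproduce the plan's figures.**

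- Respiration: 71.80/97.61 = 0.736. A two-sample t-test with 30 per arm has power 0.800 at this difference, as stated.
- Correlations, by Fisher z: r = tanh[(1.960 + 0.842)/√(n − 3)].
  - n = 30: tanh(2.802/√27) = tanh(0.539) = 0.492.
  - n = 60: tanh(2.802/√57) = tanh(0.371) = 0.355.

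Both correlations reproduce, but 0.49 belongs to one arm of 30 (with stratification) and 0.35 to all 60 (without). Section 2.4.1 assigns them the other way round.

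**Step 2: correlation produced by arm shifts alone.** Take unit variance and zero correlation within each arm, with equal arms. Over both arms the covariance is d1·d2/4 and the variances are 1 + d1²/4 and 1 + d2²/4, so

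ρ = (d1·d2/4) / √[(1 + d1²/4)(1 + d2²/4)].

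With d1 = d2 = 0.74, d²/4 = 0.1369 and ρ = 0.1369/1.1369 = 0.120. If an outcome falls under nitrite, as fatigability should, the sign reverses and the two-sided result is the same.

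**Step 3: rejection rate.** With n = 60 the test statistic is centred at atanh(ρ)·√57. For d2 = 0.74 this is 0.1210 × 7.550 = 0.914, and Φ(0.914 − 1.960) + Φ(−0.914 − 1.960) = 0.148 + 0.002 = 0.150. The simulated columns use 100,000 trials per row with within-arm correlation 0.

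| d1 (respiration) | d2 (activity, assumed) | ρ | Fisher z | Pearson | Spearman | Arm-adjusted |
|---|---|---|---|---|---|---|
| 0.74 | 0 | 0 | 5.0% | 5.0% | 5.0% | 5.1% |
| 0.74 | 0.3 | 0.051 | 6.8% | 6.7% | 6.7% | 5.0% |
| 0.74 | 0.5 | 0.084 | 9.8% | 9.9% | 9.6% | 5.1% |
| 0.74 | 0.74 | 0.120 | 15.0% | 15.4% | 15.2% | 5.1% |
| 1.0 | 1.0 | 0.200 | 33.4% | 34.2% | 35.0% | 5.1% |

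The critical |r| at n = 60 is 0.254. The expected correlation reaches it only when both effects are about 1.17.

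**Step 4: price of adjusting for arm.** At a true within-arm correlation of 0.35 with no arm shift, simulated power is 79.1% unstratified and 78.4% adjusted for arm. It is about 48% in one arm of 30. The detectable correlation moves from 0.355 to tanh(2.802/√56) = 0.358 with arm, and to tanh(2.802/√54) = 0.364 if both baselines are also in the adjustment.

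**The case against.** The strongest reply is that the paragraph already uses arm. The sentence that allows the unstratified correlation also plans the stratified one, and the paragraph adds a Fisher z comparison and a regression with treatment group. For energetics, the change coefficient in that regression is an arm-adjusted association over all participants. This stands: a reader who infers that the H3b plan as a whole ignores arm goes further than the text allows. These analyses leave gaps, however. The within-arm correlations have 30 participants each. Fisher's z asks whether the two arms' correlations differ, not whether a common one exists. The regression lists energetics but not perfusion as the change predictor, although H3b covers both. Fatigability is not named among its outcomes, though the shorthand for function and activity may be meant to include it.

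Second, no analysis is designated as decisive and Aim 3 is exploratory, so there is no formal decision rule whose error rate is breached. This also stands, and it limits the weight of the point. The missing order of precedence is itself the gap.

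Third, H3b speaks of changes induced by nitrite, so a shared arm shift is relevant to its wording. It is, but H1a and H3a already test those shifts, and a shift in both means does not show that individual changes track each other. This is a reason to keep the unstratified correlation as description.

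Fourth, several pairings of measures will be examined. Four independent tests at 0.05 would give 1 − 0.95⁴ = 18.5% familywise error, and arm adjustment does nothing about that. The results should therefore stay labelled exploratory.

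**Conclusion.** The point holds as a modest, cheaply corrected weakness in an exploratory aim. The unstratified correlation does not isolate individual-level association, the baseline-adjusted partial correlations do not repair it, and no planned arm-adjusted analysis over all participants covers perfusion.

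With 0.74 on respiration, the rejection rate with no individual-level link is about 7%, 10% and 15% for activity effects of 0.3, 0.5 and 0.74. These figures rest on bivariate normal changes, 30+30 completers, and activity effects that are assumptions.

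A reader might infer that a nitrite effect on both means makes the unstratified correlation significant. The plan's own figures do not support that. With 0.74 on both measures, about 85% of such trials remain non-significant, and 85% rejection needs effects of about 1.5 on both, which nothing in the documents suggests.

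The reversed order of 0.49 and 0.35 is a separate wording error. It matters here because the better sensitivity belongs to the all-completer analysis, which as planned is the version open to this mixing.

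**What to change.** In the Aim 3 (H3b) paragraph of section 2.4.2:

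- Name the partial correlation adjusted for treatment arm and the two baseline values, over all completers, as the main H3b analysis. Apply it to energetics and to perfusion, each against activity and fatigability, and keep the exploratory label.
- Keep the unstratified correlations, the within-arm correlations and the Fisher z comparison as descriptive.

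In section 2.4.1, attach the n = 60 detectable correlation (about 0.35; 0.36 after the adjustments) to the arm-adjusted analysis and the n = 30 figure (about 0.49) to the within-arm ones.

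The cost is a few sentences of wording and one degree of freedom for arm, under 1 point of power at a correlation of 0.35. The baseline terms are already under consideration in the plan. No new data are needed.
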